**Fractional Polynomials (Exploratory Analysis)**

The role of free sST2 on the effectiveness of GSK3772847 with respect to loss of asthma control will be investigated, using the modified intent to treat (loss of control) population. The number of participants experiencing loss of control will be predicted at each level of baseline free sST2 based on a model including a free sST2 main effect term and an interaction with treatment term.

Baseline free sST2 will be transformed using a first order fractional polynomial term, and then a second order fractional polynomial term which will be included in the model as a continuous covariate. A treatment group by transformed free sST2 covariate interaction will also be included in the model to allow the magnitude of the treatment difference to differ by baseline free sST2.

The impact of extreme observations are a well-known problem with fraction polynomial modelling. To address this a two-step transformation to “pull-in” extremes and shift the origin away from zero will be used (Royston and Sauerbrei, 2007). The formula to achieve this is given below:

$$g\delta(x) = \delta + (1 - \delta) \frac{g(x) - g(x_{(2)})}{g(x_{(1)}) - g(x_{(2)})}$$

$$\text{where } g(x) = \left[ \ln \left( \frac{\Phi\left(\frac{(x-R)}{\varepsilon}\right) + \varepsilon}{1 - \Phi\left(\frac{(x-R)}{\varepsilon}\right) + \varepsilon} \right) + \varepsilon^* \right] / (2\varepsilon^*)$$

with:  $0 < \delta < 1$

$\varepsilon = 0.01$

$\varepsilon^* = -\ln [\varepsilon/(1 + \varepsilon)]$

$$\bar{x} = n^{-1} \sum x_i$$

$$s = (n-1)^{-1} \sum (x_{(i)} - \bar{x})^2$$

As recommended we shall use  $\alpha = 0.01$  and  $\delta = 0.2$ .

All models (first and second order) will be evaluated and the best fitting model will be selected based on the AIC.

The selected best fitting model will be used to predict the probability of loss of control by treatment arm along with the corresponding predicted odds ratio by baseline free sST2. This model will include the OM option which will use the analysis dataset.

The fit of the model to the raw data will be assessed visually by overlaying a plot of the treatment estimates and differences estimated in groups defined by quartiles of baseline free sST2 counts. Estimates will be plotted against the mean baseline free sST2 count within each subgroup.

## 10.2. Exploratory Biomarker Analyses

### 10.2.1. Endpoint / Variables

- Changes from baseline in induced sputum biomarkers (subset) at weeks 8 and 16.
- Changes from baseline in exploratory serum markers at weeks 8 and 16.

### 10.2.2. Summary Measure

Change from baseline

### 10.2.3. Population of Interest

The exploratory biomarker analyses will be based on the modified Intent to Treat population, unless otherwise specified.

### 10.2.4. Strategy for Intercurrent (Post-Randomisation) Events

Not applicable.

### 10.2.5. Statistical Analyses / Methods

Details of the planned displays are provided in [Appendix 10: List of Data Displays](#) and will be based on GSK Data Standards and statistical principles.

Induced sputum biomarkers and exploratory serum markers at weeks 8 and 16 will be summarised using descriptive statistics, including the geometric mean and CV as well as listed.

No statistical analysis will be performed on this data.

## **12. APPENDICES**

### **12.1. Appendix 1: Protocol Deviation Management**

The full list of protocol deviations collected on the eCRF is in the PDMP. Please refer to this document for current guidance.

There is no per protocol population in this study.

12.2. Appendix 2: Schedule of Activities

12.2.1. Protocol Defined Schedule of Events

Procedure	Pre-Screening 	Screen Run-in	Treatment Period										Follow-up Period  (± 3 days)			Notes
			± 2 days			± 3 days							12	13	14	
Visit	0	1	2 	3	4	5	6	7	8	9	10	11 (ETP or EW)	12	13	14	1. Pre-screening and screening can occur on the same day 2. FU period to start 4 weeks after ETP or EW visit. 3. Visit 2 = Day 1 (first dose of IP).
Week	-4~-2	-2	0	1	2	4	6	8	10	12	14	16	20	24	28	
Study Day	-28~-14	-14	1	8	15	29	43	57	71	85	99	113				
Informed consent (ICF)	X															
Genetic ICF		X														
ICF for sputum		X														
Inclusion and exclusion criteria		X														
Randomisation Criteria			X													
Demography	X															
Full physical exam including height and weight		X														
Medical history (includes substance abuse)		X														Substances [Drugs, Alcohol, tobacco] and family history of premature CV disease]: [including cardiovascular medical history]
Laboratory																

Procedure	Pre-Screening 	Screen Run-in	Treatment Period										Follow-up Period  (± 3 days)			Notes
			± 2 days			± 3 days										
Visit	0	1	2 	3	4	5	6	7	8	9	10	11 (ETP or EW)	12	13	14	1. Pre-screening and screening can occur on the same day 2. FU period to start 4 weeks after ETP or EW visit. 3. Visit 2 = Day 1 (first dose of IP).
Week	-4~-2	-2	0	1	2	4	6	8	10	12	14	16	20	24	28	
Study Day	-28~-14	-14	1	8	15	29	43	57	71	85	99	113				
Laboratory assessments		X 	X 	X	X 	X 	X	X 	X	X 	X	X 			X 	Haematology (including eosinophil count) and cardiac markers measured at all clinic visits. 1. Clinical chemistry (including liver chemistry). 2. Routine urinalysis at screening (Visit 1)
Pregnancy test 		X 	X 			X 		X 		X 		X	X	X	X	1. Test for women with child bearing potential. 2. Serum pregnancy test at V0/V1. 3. Test to be performed pre-dose during the treatment period.
[HIV, Hep B and Hep C screen]		X														A confirmatory negative Hepatitis C RNA test must be obtained, to be able to enrol participants with positive Hepatitis C antibody due to prior resolved disease. If test has been performed within 3 months prior to first dose of study treatment, testing at screening is not required.

Procedure	Pre-Screening 	Screen Run-in	Treatment Period										Follow-up Period  (± 3 days)			Notes
			± 2 days			± 3 days							12	13	14	
Visit	0	1	2 	3	4	5	6	7	8	9	10	11 (ETP or EW)	12	13	14	1. Pre-screening and screening can occur on the same day 2. FU period to start 4 weeks after ETP or EW visit. 3. Visit 2 = Day 1 (first dose of IP).
Week	-4~-2	-2	0	1	2	4	6	8	10	12	14	16	20	24	28	
Study Day	-28~-14	-14	1	8	15	29	43	57	71	85	99	113				
Genetic blood sample – Pre dose							X									Pharmacogenetic sample may be drawn any time from Visit 2 onwards. Informed consent for optional substudies e.g. genetics must be obtained before collecting a sample
Sputum sample collection			X					X				X				Pre-dose collection and in a sub-set of participants (~50 %) at selected sites; also collected for EW participants
PK, target engagement and immunogenicity assessments			X	X	X	X		X		X		X	X	X	X	See SoA Table 2 for details
Exploratory Biomarkers			X					X				X				Pre dose collection
Efficacy																
Spirometry		X	X		X	X	X	X	X	X	X	X				Test to be performed pre-dose during the Treatment period
Reversibility		X														
FeNO			X	X	X	X	X	X	X	X	X	X				Test to be performed pre-dose
Review loss of asthma control criteria				X	X	X	X	X	X	X	X	X				It will include review of data to determine loss of asthma control. See Section 9.1.5.
Dispense eDiary		X														

Procedure	Pre-Screening 	Screen Run-in	Treatment Period										Follow-up Period  (± 3 days)			Notes
			± 2 days			± 3 days							12	13	14	
Visit	0	1	2 	3	4	5	6	7	8	9	10	11 (ETP or EW)	12	13	14	1. Pre-screening and screening can occur on the same day 2. FU period to start 4 weeks after ETP or EW visit. 3. Visit 2 = Day 1 (first dose of IP).
Week	-4~-2	-2	0	1	2	4	6	8	10	12	14	16	20	24	28	
Study Day	-28~-14	-14	1	8	15	29	43	57	71	85	99	113				
Collect eDiary												X				
Review eDiary			X	X	X	X	X	X	X	X	X	X				
Safety																
12-lead ECG		X	X 			X 		X 		X 		X				1. Test to be performed pre-dose and post-dose within 30 mins after end of infusion.
24 hrs Holter		X	X 			X 				X 						Holter monitor needs to be returned to clinic at end of 24-hour recording (i.e. the next day). 1. Place the Holter 30-60 mins prior to dosing.
Vital signs		X	X 	X	X	X 	X	X 	X	X 	X	X	X	X	X	1. Test to be performed pre-dose prior to spirometry and post-dose prior the 12-lead ECG.
Dispense paper Medical Problems/Medications Taken worksheet		X	X	X	X	X	X	X	X	X	X	X	X	X		
Review paper Medical Problems/Medications Taken worksheet			X	X	X	X	X	X	X	X	X	X	X	X	X	

Procedure	Pre-Screening 	Screen Run-in	Treatment Period										Follow-up Period  (± 3 days)			Notes
			± 2 days			± 3 days							12	13	14	
Visit	0	1	2 	3	4	5	6	7	8	9	10	11 (ETP or EW)	12	13	14	1. Pre-screening and screening can occur on the same day 2. FU period to start 4 weeks after ETP or EW visit. 3. Visit 2 = Day 1 (first dose of IP).
Week	-4~-2	-2	0	1	2	4	6	8	10	12	14	16	20	24	28	
Study Day	-28~-14	-14	1	8	15	29	43	57	71	85	99	113				
AE/SAE review	X 	X 	←-----→										X	X	X	1. At V0 and V1 collect only SAEs considered as related to study participation.
Concomitant medication review	X	X	←-----→										X	X	X	
Questionnaires																
ACQ-5		X	X													After randomization, ACQ5 will be completed by the participants every 7 days.
SGRQ			X			X		X		X		X				
Study Treatment																
Double blind Study Treatment (IP)			X			X		X		X						Patients will remain in the clinic for monitoring for at least 2 hours after the end of infusion.
FP/Sal (500/50) dispensing		X	X													
FP (mcg) dispensing					500	250	100	50								
Dispense albuterol (as needed)		X	X	X	X	X	X	X	X	X	X	X				

Procedure	Treatment Period										Follow-up  (± 3 days)			Notes
	± 2 days			± 3 days										
Visit	2 	3	4	5	6	7	8	9	10	11 (ETP or EW)	12	13	14	1. Visit 2 = Day 1 (first dose of IP). 2. FU period to start 4 weeks after ETP or EW visit.
Week	0	1	2	4	6	8	10	12	14	16	20	24	28	
Study Day	1	8	15	29	43	49	71	85	99	113				
Double blind Study Treatment (IP)	X			X		X		X						
PK sample	X 	X	X	X 		X 		X 		X	X	X	X	1. Pre dose and post dose. 2. Post dose only. 3. Pre dose only. Pre-dose samples within 2 hours from the planned dosing time. Post-dose samples as soon as possible after end of infusion but must be taken within 4 hours.
Free and total sST2	X 	X	X	X 		X 		X 		X	X	X	X	
Immunogenicity sample	X 		X	X 		X 		X 		X	X	X	X	

**12.3. Appendix 3: Assessment Windows**

**12.3.1. Definitions of Assessment Windows for Analyses**

Nominal visits will be used and no windowing will be applied for analysis.

## 12.4. Appendix 4: Study Phases and Treatment Emergent Adverse Events

### 12.4.1. Study Phases

Assessments and events will be classified according to the time of occurrence relative to study treatment start date.

Study Phase for all data except efficacy	Definition
Pre-treatment	Date $\leq$ Study Treatment Start Date
On-treatment	Study Treatment Start Date < Date $\leq$ Study Treatment Stop Date + 28 days
Post-treatment	Date > Study Treatment Stop Date + 28 days

Study Phase for efficacy	Definition
Pre-treatment	Date $\leq$ Study Treatment Start Date
On-treatment	Study Treatment Start Date < Date $\leq$ Date of discontinuation from study treatment Or if the participant did not discontinue early from study treatment Study Treatment Start Date < Date $\leq$ Study Treatment Stop Date + 28 days
Post-treatment	Date > Study Treatment Stop Date + 28 days

Once participants withdraw from study treatment they immediately restart their standard of care medication (ICS/LABA). As a result, any data collected past this point will have been impacted by the standard of care medications and any estimates produced biased by the additional use of ICS/LABA. For this reason, data post withdrawal from study treatment is not included in the on-treatment efficacy analysis.

The post treatment definition is the same for efficacy and safety analysis.

Completion of study epoch's will be defined as the following:

Study Phase	Definition of Completion
Run-in	Randomised into study and received first dose of study treatment
Treatment	Completed Week 16 visit or withdrew from treatment phase due to loss of asthma control
Follow up	Completed 12 week follow-up period

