### 12.4.2. Treatment Emergent Flag for Adverse Events

Flag	Definition
Treatment Emergent	
If AE onset date is on or after treatment start date & on or before treatment stop date + 28 days.
 
Study Treatment Start Date ≤ AE Start Date ≤ Study Treatment Stop Date + 28 days

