**12.7.2.1. Handling of Missing and Partial Dates**

Element	Reporting Detail
General	
 
● Partial dates will be displayed as captured in subject listing displays.
 

Adverse Events	
 
● The eCRF allows for the possibility of partial dates (i.e., only month and year) to be recorded for AE start and end dates; that is, the day of the month may be missing. In such a case, the following conventions will be applied for calculating the time to onset and the duration of the event:                             
 
○ Missing Start Day: First of the month will be used unless this is before the start date of study treatment; in this case the study treatment start date will be used and hence the event is considered On-treatment as per Appendix 4: Study Phases and Treatment Emergent Adverse Events.
 
○ Missing Stop Day: Last day of the month will be used, unless this is after the stop date of study treatment; in this case the study treatment stop date will be used.
 
 
 
● Completely missing start or end dates will remain missing, with no imputation applied. Consequently, time to onset and duration of such events will be missing.
 

Concomitant Medications/ Medical History	
 
● Partial dates for any concomitant medications recorded in the CRF will be imputed using the following convention:                             
 
○ If the partial date is a start date, a '01' will be used for the day and 'Jan' will be used for the month
 
○ If the partial date is a stop date, a '28/29/30/31' will be used for the day (dependent on the month and year) and 'Dec' will be used for the month.
 
 
 
● The recorded partial date will be displayed in listings.
 

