## 12.10.7. Safety Tables

Safety: Tables					
No.	Population	IDSL / Example Shell	Title	Programming Notes	Deliverable [Priority]
Adverse Events (AEs)					
3.1.	SAFF_ALL	SAFE_T01	Overview of On-treatment Adverse Events During the Study		ETP, SAC
3.2.	SAFF_ALL	AE1	Summary of All On-treatment Adverse Events by System Organ Class and Preferred Term	ICH E3	ETP, SAC
3.3.	SAFF_ALL	AE1	Summary of All Post-treatment Adverse Events by System Organ Class and Preferred Term	ICH E3	ETP, SAC
3.4.	SAFF_ALL	AE1	Summary of All On-treatment Adverse Events Leading to Permanent Discontinuation of Study Treatment by System Organ Class and Preferred Term	ICH E3	ETP, SAC
3.5.	SAFF_ALL	AE1	Summary of All On-treatment Adverse Events Leading to Withdrawal from Study by System Organ Class and Preferred Term	ICH E3	ETP, SAC
3.6.	SAFF_ALL	AE1	Summary of All On-treatment Fatal Adverse Events by System Organ Class and Preferred Term	ICH E3	ETP, SAC
3.7.	SAFF_ALL	AE3	Summary of All On-treatment Common ( $\geq 3\%$ ) Adverse Events by Overall Frequency	ICH E3	ETP, SAC
3.8.	SAFF_ALL	AE1	Summary of All On-treatment Drug-Related Adverse Events by System Organ Class and Preferred Term	ICH E3	ETP, SAC
3.9.	SAFF_ALL	AE15	Summary of All On-treatment Common ( $\geq 3\%$ ) Non-serious Adverse Events by System Organ Class and Preferred Term (Number of Participant and Occurrences)	FDAAA, EudraCT	ETP, SAC
3.10.	SAFF_ALL	AE1	Summary of All Pre-treatment Serious Adverse Events by System Organ Class and Preferred Term		ETP, SAC

Safety: Tables					
No.	Population	IDSL / Example Shell	Title	Programming Notes	Deliverable [Priority]
3.11.	SAFF_ALL	AE1	Summary of All On-treatment Serious Adverse Events by System Organ Class and Preferred Term	ICH E3	ETP, SAC
3.12.	SAFF_ALL	AE1	Summary of All Post-treatment Serious Adverse Events by System Organ Class and Preferred Term	ICH E3	ETP, SAC
3.13.	SAFF_ALL	AE16	Summary of All On-treatment Serious Adverse Events by System Organ Class and Preferred Term (Number of Participants and Occurrences)	FDAAA, EudraCT	ETP, SAC
3.14.	SAFF_ALL	AE1	Summary of All On-treatment Serious Adverse Events Leading to Permanent Discontinuation of Study Treatment by System Organ Class and Preferred Term	IDSL	ETP, SAC
3.15.	SAFF_ALL	AE1	Summary of All On-treatment Serious Adverse Events Leading to Withdrawal from Study by System Organ Class and Preferred Term	IDSL	ETP, SAC
Adverse Events of Special Interest (AESIs)					

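### An adverse event on the first infusion day is pre-treatment under SAP 12.4.1 but on-treatment under 12.4.2 and 12.7.2.1, and the SAP does not say which rule fills the on-treatment tables

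*SAP*

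**What the plan says.** Section 12.4.1 of the current (amended) plan opens with a scope that names events as well as measurements: "Assessments and events will be classified according to the time of occurrence relative to study treatment start date". For all data except efficacy, pre-treatment is "Date $\leq$ Study Treatment Start Date" and on-treatment is "Study Treatment Start Date < Date $\leq$ Study Treatment Stop Date + 28 days". The start date itself therefore belongs to pre-treatment.

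Section 12.4.2 gives the treatment-emergent flag for AEs: "If AE onset date is on or after treatment start date", written out as "Study Treatment Start Date ≤ AE Start Date ≤ Study Treatment Stop Date + 28 days". Here the start date is inside the window.

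Section 12.7.2.1 deals with AEs that have a month and year but no start day. If the first of the month falls before treatment began, "in this case the study treatment start date will be used and hence the event is considered On-treatment", with Appendix 4 cited as the authority. Appendix 4 contains both 12.4.1 and 12.4.2.

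In Section 12.10.7, Tables 3.1 to 3.19 are labelled by phase. The only pre-treatment one is Table 3.10, "Summary of All Pre-treatment Serious Adverse Events by System Organ Class and Preferred Term". The AESI tables (3.16 to 3.19) are on-treatment or post-treatment only.

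For a missing AE stop day, Section 12.7.2.1 uses the last day of the month unless that is after the stop date of treatment; "in this case the study treatment stop date will be used".

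**The concern.** On-treatment is a phase name that 12.4.1 defines, and the safety tables use that name. None of them is titled treatment emergent. A programmer who applies the defined term to the table titles would place Day 1 events outside the on-treatment tables. A programmer who applies the AE flag would place them inside. Both can claim to have followed the plan.

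The day in question matters. Section 12.6.4 lists hypersensitivity, anaphylactic reaction and angioedema among the AESIs, and the schedule of activities keeps participants under observation for at least 2 hours after each infusion. Day 1 is one of four planned infusions and the only one for a participant who stops before Week 4. At stake is whether AE and AESI incidence, which serves a stated secondary objective, includes reactions to the first infusion.

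The stop-day rule raises a smaller point: it can produce an end date earlier than the onset date.

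**Working it through.** **Inputs.** The first dose is on Day 1 and the last planned dose is at Week 12, Day 85 (schedule of activities, Section 12.2.1). The on-treatment window closes 28 days after the stop date (12.4.1 and 12.4.2). The stop date is taken as the date of the last infusion, because Section 12.6.2 says that the eCRF treatment dates are those of the physical infusion. The window therefore closes on Day 85 + 28 = Day 113.

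**The two rules side by side, four doses.**

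| AE start day | Phase under 12.4.1 | Treatment emergent under 12.4.2 |
|---|---|---|
| −1 | Pre-treatment | No |
| 1 | **Pre-treatment** | **Yes** |
| 2, 29, 57, 85, 113 | On-treatment | Yes |
| 114 | Post-treatment | No |

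For a participant with a single dose the window closes on Day 1 + 28 = Day 29. Days 2 and 29 are in under both rules and Day 30 is out under both. Day 1 is again pre-treatment under one rule and treatment emergent under the other. Over every day from −28 to 199, Day 1 is the only disagreement.

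**What follows in the tables if 12.4.1 selects the events.**

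- A non-serious Day 1 AE is pre-treatment. No phase-labelled table takes pre-treatment non-serious AEs, so it enters none of Tables 3.1 to 3.19. If it ended treatment, it also misses Table 3.4.
- A Day 1 AESI enters none of Tables 3.16 to 3.19.
- A Day 1 serious AE moves from Table 3.11 to Table 3.10 and is presented as preceding treatment.
- All of these remain in Listing 13 (all AEs), and AESIs and serious events also remain in Listings 17, 18 and 21, whose titles carry no phase restriction.

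Tables 3.20 and 3.21 (suspected product reactions in Mexican and in other participants) have no phase label. A Day 1 event judged related might be counted there, but they do not stand in for the main AE or AESI tables.

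If the AE phase rule used the 12.4.2 inequality, the days of disagreement would fall from one to none.

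**The stop-day rule.** Take an AE that starts on Day 99 (the Week 14 visit), after a last infusion on Day 85, with only the month of its end recorded. The last day of that month is after Day 85, so the end is set to Day 85. End minus onset is 85 − 99 = −14 days. The same happens to any AE with a month-only end date that starts after the last infusion. For a participant with all four doses, that period runs from Week 12 to the last visit at Week 28, which is 28 − 12 = 16 weeks.

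**The case against.** The AE-specific text points one way. Section 12.4.2 includes Day 1. Its note on a missing stop date uses the word on-treatment for the flagged event, and 12.7.2.1 does the same for an event moved to the start date. Section 12.4.1 is the general rule, and a specific rule usually prevails over a general one. Table 3.10 fits this reading: at the pre-screening and screening visits only serious events related to study participation are collected, so a serious-only pre-treatment table is what one would expect if pre-treatment means before Day 1. This argument stands as evidence of intent. It does not settle the matter, because the SAP never states the precedence and the table titles use the phase name.

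A reader might infer that everything dated Day 1 is misfiled. The document does not support that. Concomitant medication has its own rule in 12.4.1.1, which counts the first dose date as on-treatment. Baseline measurements on Day 1 are rightly pre-dose. The Week 0 changes from pre-dose to post-dose in vital signs and ECG are planned by timepoint in Section 8.3, so they are not lost.

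A reader might also infer that the safety comparison is biased toward no difference, or put a number on the events lost per arm. The SAP gives no rate of same-day reactions and no excess on active drug. If equal numbers were removed from equal arms, the risk difference would not change. Neither a direction of bias nor a count can be supported.

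On the stop-day rule, it is fair to say that no planned safety table visibly depends on AE duration. Phase is assigned by onset, so incidence is unaffected.

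**Conclusion.** The contradiction is real and is in the current text. It concerns one day, Day 1, and AE and AESI summaries only. Its consequence is conditional: Day 1 reactions leave the on-treatment summaries if the tables are selected by the 12.4.1 phase, and they do not if the 12.4.2 flag is used. The second reading is probably the intended one, but the SAP does not say so. Even on the first reading nothing leaves the listings. No primary or efficacy result is touched.

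The stop-day rule is wrong as written for AEs that begin after the last infusion. Its effect is confined to durations of events with month-only end dates, on the assumption that the treatment stop date is the last infusion date.

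This should be fixed, but it does not threaten the trial's main conclusions.

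**What to change.** 1. For AEs, define pre-treatment as AE start date < treatment start date, and on-treatment as treatment start date ≤ AE start date ≤ treatment stop date + 28 days, as in 12.4.2. Where onset time is collected, use it relative to the infusion for Day 1 events.
2. State in Section 8.1 or 12.10.7 that every AE and AESI table labelled on-treatment uses this definition. The Appendix 4 reference in 12.7.2.1 then becomes correct.
3. Leave the concomitant medication rule in 12.4.1.1 as it is.
4. For a missing AE stop day, impute the last day of the month, capped at the date of study completion or withdrawal and never before onset.

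The cost is a few lines of SAP wording and a change to the AE phase flag and one imputation rule. No new data are needed. It is best settled before unblinding, so that the choice of rule cannot be seen as driven by the results.

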### 12.6.2. Study Population

Age
Date of birth will be set as PPD YYYYY where YYYYY is the year of birth taken from the CRF. For participants who attended a screening visit, age will be calculated at the screening visit date. For pre-screen failures, age will be calculated at the pre-screening visit date.
Body Mass Index (BMI)
BMI = Weight (kg) / Height(m) 
Treatment Misallocations
To allocate treatment, the number of doses of GSK3772847 and Placebo that were given will be calculated, and the subject will be assigned to whichever treatment has the higher number. The only exception will be when both treatments were given equally, in which case the subject will be assigned their randomised treatment.
Early Withdrawal from Study Treatment Date

The eCRF captures the study treatment start and end, however this is the physical time and date of the infusion. The date of early withdrawal from study treatment is not captured and should therefore be calculated as follows:
 
 
• If the participant withdrew from treatment due to loss of asthma control then the date of early withdrawal from study treatment is set to the date of loss of asthma control.
 
• If the participant withdrew due to an AE/SAE/Death then withdrawal date is set to the AE/SAE onset date (all deaths should be reported as serious adverse events)
 
• If the participant withdrew from study treatment (for a reason other than those above) during the first 10 weeks of the study i.e. during the down titration of the background medications, then the FP/SAL or FP discontinuation date should be used as the date of withdrawal from study treatment.
 
• For participants who withdraw from study treatment (for a reason other than those above) between Week 10 and Week 16, there is no information on when they withdrew as they are no longer taking background medications. The date of early withdrawal from study treatment should therefore be set to the maximum of date of last dose of FP and date of last dose +1. This is because no more information is available other than the fact that they had not lost control prior to completing the down titration or prior to receiving their final dose of IP.
 

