## 12.7. Appendix 7: Reporting Standards for Missing Data

### 12.7.1. Premature Withdrawals

Element	Reporting Detail
General	
 
• Subject study completion (i.e. as specified in the protocol) was defined as either completing the 16 week treatment period and three month safety follow up, or withdrawing from the treatment period early due to loss of asthma control and completing the three month safety follow up period.
 
• Withdrawn participants were not replaced in the study, unless the participants were withdrawn due to sites failing to comply with GCP.
 
• All available data from participants who were withdrawn from the study will be listed and all available planned data will be included in summary tables and figures, unless otherwise specified.
 
• Withdrawal visits will be slotted as per Appendix 3: Assessment Windows or will be summarised as withdrawal visits.
 

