## 12.10.9. Pharmacodynamic and Biomarker Tables

Pharmacodynamic and Biomarker: Tables					
No.	Population	IDSL / Example Shell	Title	Programming Notes	Deliverable [Priority]
Secondary: Pharmacodynamic					
6.1.	mITT		Summary of Raw and Percentage Change from Baseline in Free Soluble ST2 concentration (ug/L) (On-treatment)	Pre and Post dose.	ETP, SAC
6.2.	mITT		Analysis of Percentage Change from Baseline in Free Soluble ST2 concentration (ug/mL) (On-treatment)	Pre dose only.	ETP, SAC
6.3.	mITT		Summary of Raw and Percentage Change from Baseline in Free soluble ST2 concentration (ug/L) (Post-treatment)		ETP, SAC
6.4.	mITT		Analysis of Percentage Change from Baseline in Free soluble ST2 concentration (ug/mL) (Post-treatment)		ETP, SAC
6.5.	mITT		Summary of Raw and Percentage Change from Baseline in Total Soluble ST2 concentration (ug/L) (On-treatment)	Pre and Post dose.	ETP, SAC
6.6.	mITT		Analysis of Percentage Change from Baseline in Total Soluble ST2 concentration (ug/L) (On-treatment)	Pre dose only.	ETP, SAC
6.7.	mITT		Summary of Raw and Percentage Change from Baseline in Total Soluble ST2 concentration (ug/L) (Post-treatment)		ETP, SAC
6.8.	mITT		Analysis of Percentage Change from Baseline in Total Soluble ST2 concentration (ug/L) (Post-treatment)		ETP, SAC
Exploratory: Biomarkers					
6.9.	mITT		Summary and Change from Baseline in Induced Sputum Biomarkers (subset) at Weeks 8 and 16	Include geometric mean and %CV	ETP, SAC
6.10.	mITT		Summary and Change from Baseline in Exploratory Serum Markers at Weeks 8 and 16	Include geometric mean and %CV	ETP, SAC

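### The on-treatment phase ends exactly 28 days after the last infusion, so an in-window Week 16 visit can be classed post-treatment; the handling of early-withdrawal visits is also left open

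*SAP*

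**What the plan says.** Section numbers are those of the amended plan, which comes first in the SAP file.

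- **Phase rule (12.4.1).** One table covers efficacy data and another covers all other data. On-treatment runs up to and including stop date + 28 days for all non-efficacy data, and for the efficacy data of participants who did not discontinue early. In both tables post-treatment is "Date > Study Treatment Stop Date + 28 days", and the text adds: "The post treatment definition is the same for efficacy and safety analysis".
- **Epochs (12.4.1).** The same section treats attendance at the Week 16 visit as finishing the treatment epoch.
- **Stop date (12.6.2).** "The eCRF captures the study treatment start and end, however this is the physical time and date of the infusion".
- **Schedule (12.2.1).** The last infusion is at Week 12, Day 85. Visit 11 is at Week 16, Day 113. The later treatment visits carry ±3 days. The Visit 11 column serves both the end of the treatment phase and early withdrawal.
- **Where the phase is used.** sST2 has separate on-treatment and post-treatment repeated-measures models (10.1.5) and displays (Tables 6.1–6.8 in 12.10.9). Tables 2.14 (hospitalisations and ER visits) and 2.23 (exacerbations) are titled as on-treatment.
- **Withdrawal visits (12.7.1).** "Withdrawal visits will be slotted as per" Appendix 3, "or will be summarised as withdrawal visits". Appendix 3 (12.3.1) says: "Nominal visits will be used and no windowing will be applied for analysis".

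**The concern.** The cut-off equals the planned interval between the last infusion and the Week 16 visit, with no allowance for the visit windows. A participant who takes all four doses and attends Week 16 within window can still have that visit labelled post-treatment because of a day or two of scheduling. The label then decides which sST2 model the sample enters and whether an event just before Week 16 appears in an on-treatment display. It also sits badly with the epoch definition in the same section.

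The second strand is the Visit 11 label. With no analysis windows and two alternatives for withdrawal visits, the plan does not settle whether an early-withdrawal assessment, made at any earlier study day, is summarised as Week 16.

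**Working it through.** **1. The plan's own interval.** Planned gap: 113 − 85 = 28 days. The exposure formula in 12.6.2 agrees: 85 − 1 + 29 = 113. A visit exactly on plan falls on the last on-treatment day.

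**2. Permitted gaps.** Let e12 and e16 be the deviations in days from Day 85 and Day 113, each from −3 to +3. Gap = 28 + e16 − e12, so it runs from (113 − 3) − (85 + 3) = 22 to (113 + 3) − (85 − 3) = 34 days. The visit is post-treatment when the gap exceeds 28, that is, when e16 > e12.

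**3. Share affected.** The SAP gives no distribution of visit dates, so these are assumptions. For independent deviations with the same distribution, share = (1 − P(e16 = e12)) / 2.

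| Assumption for each visit | P(tie) | Share post-treatment |
|---|---|---|
| Uniform over ±3 days | 7/49 | 21/49 = 42.9% |
| Triangular over ±3 days | 44/256 | 41.4% |
| 50% on the planned day, rest spread evenly | 0.25 + 0.25/6 = 0.292 | 35.4% |
| 70% on the planned day | 0.49 + 0.09/6 = 0.505 | 24.8% |
| 80% on the planned day | 0.64 + 0.04/6 = 0.647 | 17.7% |
| 90% on the planned day | 0.81 + 0.01/6 = 0.812 | 9.4% |

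The schedule's header shows both ±2 and ±3 days, and the column breaks are hard to read in the extracted table. If ±2 applied to both visits, the uniform case would be 10/25 = 40%. With Week 16 uniform over ±3 days, the share is 6/7 = 85.7% after a Week 12 dose given 3 days early, 3/7 = 42.9% after one on plan, and 0% after one 3 days late.

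**4. sST2.** Samples are scheduled at Week 16 and at follow-up Weeks 20, 24 and 28. Under the date rule, Week 16 samples taken 22–28 days after the last infusion enter the on-treatment model, and those taken 29–34 days after enter the post-treatment model. Each model has visit and treatment-by-visit terms and an unstructured covariance. The on-treatment Week 16 estimate therefore rests on the participants with shorter gaps, and the post-treatment model gains a partial Week 16 level.

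**5. Event displays.** An exacerbation or hospitalisation after day 28 but on or before an in-window Week 16 visit drops out of Tables 2.14 and 2.23.

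**6. By-visit efficacy summaries.** Section 7.2.3 removes only data after loss of control or early withdrawal from treatment, so it keeps a completer's Week 16 value at day 30 after the last infusion. Section 12.4.1 labels the same value post-treatment. The plan does not say which rule governs.

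**7. Withdrawal visits.** One option in 12.7.1 relies on windows that Appendix 3 does not contain; the other reports these visits separately. No choice is made. Section 10.1.5 uses all sST2 data as collected, so an early-withdrawal sample carrying the Visit 11 label could enter the Week 16 level of the on-treatment model.

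**The case against.** The 28-day limit has a rationale. Section 12.6.2 treats each dose as giving 28 days of coverage, and 12.4.1.1 and 12.4.2 use the same limit for concomitant medication and treatment-emergent AEs. That stands: a blanket stop date + 34 days would remove the misclassification but break this consistency, and would stretch the phase for people who stopped dosing early. Section 12.5.2 also says planned time relative to dosing is used in summaries and analyses, and planned Week 16 is exactly day 28. That does not rescue the rule, because 12.4.1 is written in dates.

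Several stronger readings are tempting but unsupported:

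- **Week 16 events are lost from the primary endpoint.** Section 12.6.3 dates loss of control from its log page, and nothing says the phase flag filters it.
- **Week 16 FEV1, FeNO, ACQ-5 and SGRQ results rest on an accidental subset.** Section 7.2.3 defines those summaries without this cut-off. FEV1 and FeNO are modelled only to Week 4; ACQ-5 and SGRQ are descriptive. What remains is a disagreement between two sections.
- **By-visit safety tables are distorted by the cut-off.** They are by nominal week, and their titles carry no on-treatment restriction.
- **Early-withdrawal visits will be reported as Week 16.** Section 12.7.1 allows them to be summarised separately, and efficacy data after discontinuation are already excluded. The defect is an unfixed choice.
- **About 36% of Visit 11 records are early withdrawals, more of them on placebo.** That comes from (70 × 0.44 + 70 × 0.28)/140 = 50.4/140. But 28% is the minimum detectable result in section 2.6, not an expected rate; loss of control can also be found at the scheduled Week 16 visit; and an excess on placebo presupposes efficacy.

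**Conclusion.** The point holds with limited scope. It follows from the SAP's dates alone that an in-window Week 16 visit 29–34 days after the last infusion is classed post-treatment, against the epoch definition in the same section. It rests on reading the stop date as the last infusion date, which 12.6.2 supports. How often it happens is unknown: 43% is the uniform case and should not be read as an expectation; about 9–35% applies if 50–90% of visits fall on the planned day. It is zero only if no Week 16 visit falls more than 28 days after the last dose.

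The clear harm is to a secondary pharmacodynamic analysis (sST2) and two descriptive event displays, plus an inconsistency with 7.2.3 for by-visit efficacy summaries. No effect on the primary endpoint is shown. The withdrawal-visit strand is a smaller, separate ambiguity, relevant mainly to safety, PD and biomarker summaries and the sST2 model.

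**What to change.** 1. In 12.4.1, for participants who did not discontinue early, class scheduled assessments up to and including nominal Visit 11 (Week 16) as on-treatment. Align 12.4.1 with 7.2.3 in the same edit.
2. For these participants, bound on-treatment efficacy events (Tables 2.14 and 2.23) by the later of stop date + 28 days and the actual Week 16 visit date. The exposure time behind the rate in Table 2.14 should end on the same date.
3. Leave the 28-day limit unchanged for treatment-emergent AEs and for early discontinuers.
4. In 12.7.1, delete the option that refers to Appendix 3 and summarise early-withdrawal visits only as withdrawal visits, so that they do not enter Week 16 safety, PD and biomarker summaries or the sST2 model.

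The cost is SAP wording and one phase-flag derivation; no new data are needed. It should be settled before the randomisation codes are released, so that the cut-off is not chosen with results in view.
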